#### 2.3.7.2 STUDY SUCCESS

The null hypothesis is that the probability of achieving Month 60 composite clinical success (CCS) for patients implanted with the Simplify Disc device is no more than 0.10 smaller than the probability of ACDF control patients achieving Month 60 CCS. This study will be considered a success if the PS-quintile adjusted, multiple imputation based, 1-sided p-value for rejecting this null hypothesis is less than or equal to 0.05.

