# 2.3.2 STUDY HYPOTHESIS

The study hypothesis is that in subjects with intractable radiculopathy (arm pain and/or a neurological deficit) with or without neck pain or myelopathy due to a single-level abnormality localized to the level of the disc space at one level from C3 to C7 that is unresponsive to conservative management, the Month 60 composite clinical success (CCS) rate of the Simplify Disc will be no worse than conventional ACDF. Individual success for Simplify Disc and the historical control ACDF is defined as follows:

- Improvement on the NDI of at least 15 percentage points compared to baseline (pre-op) in the Simplify Disc IDE study, and
- No device failures by Month 60, and
- No subsequent surgical procedure at the index level (including revision, removal, reoperation, or supplemental fixation) by Month 60.

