# 2.3.7 STATISTICAL CONSIDERATIONS

#### 2.3.7.1 PRIMARY ENDPOINT

The study hypothesis is that in subjects with intractable radiculopathy (arm pain and/or a neurological deficit) with or without neck pain or myelopathy due to a single-level abnormality localized to the level of the disc space at one level from C3 to C7 that is unresponsive to conservative management or have the presence of progressive symptoms, the Month 60 composite clinical success (CCS) rate of the Simplify Disc will be no worse than conventional ACDF when success of ACDF is evaluated at Month 60. Individual success for Simplify Disc and the historical control ACDF is defined as follows:

- Improvement on the NDI of at least 15 percentage points compared to baseline in the Simplify Disc IDE study, and
- No device failures by Month 60, and
- No subsequent surgical procedure at the index level (including revision, removal, reoperation, or supplemental fixation) by Month 60.

Device failure is defined as breakage, migration, or mechanical failure of the components as defined in the Radiographic Evaluation Protocol. Failure of the allograft will not be counted as device failure in the historical ACDF control group.

Per FDA Guidance for the Preparation of IDEs for Spinal Systems, the following definitions apply for the PAS:

- Reoperation any surgical procedure at the index level that *does not involve* modification, addition or removal of any components of the device" in the postoperative or follow-up period.
- Revision any procedure in the postoperative or follow-up period that adjusts modifies or removes part of the original implant configuration *with or without* replacement of a component – may include adjusting the position of the original configuration in the postoperative or follow-up period.
- Removal a procedure where the entire device is removed with or without replacement of the device in the postoperative or follow-up period.

• Supplemental fixation – a procedure in which additional instrumentation not under study is implanted (e.g., supplemental placement of a rod/ screw system).

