#### 2.3.7.4 JUSTIFICATION OF CONTROL AND EXPIRMENTAL GROUP SUCCESS RATES

Based on multiple imputation and including N=150 Simplify Disc subjects and N=117 historical controls, the Month 24 PS adjusted success rates were estimated to be 93.0% and 73.6%, respectively, for a group difference of 19.4% (90% LB CI 10.9%). The lower bound of the 90% 2-sided CI is equivalent to the lower bound of the 95% 1-sided non-inferiority CI. In the completer's analysis set, 132 of 142 Simplify Disc subjects achieved Month 24 overall success, and 68 of 96 Controls achieved Month 24 overall success.

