#### 2.3.7.5 SAMPLE SIZE ANALYSIS

For the purposes of sample size calculation, it is estimated that 85% of the estimated 142 Simplify Disc subjects (N=121) who are not terminal failures or lost to follow-up by Month 24 will be available at year 5. It is estimated that 60% of the estimated 106 (N=64) Control subjects who are not terminal failures or lost to follow-up by Month 24 will be available at year 5.

Based on these results, it was conservatively estimated that the 5-year overall success rates would be 70% of the observed rates, that is, 65% and 50% for Simplify Disc and historical ACDF control, respectively. If the success rates in both groups are larger, statistical power will be larger and so this power analysis would be conservative. With sample sizes of 121 and 64, and assuming 65% and 50% success, the power to detect non-inferiority is 96% at a one-sided 0.05 significance level.

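### The primary null hypothesis is inverted: as written, the study succeeds only if Simplify is shown to be worse than ACDF by more than the 0.10 margin

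*Combined protocol and SAP*

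**What the plan says.** Section 2.3.7.2 (Study Success) sets the primary decision rule in two sentences. The null hypothesis is that the probability of Month 60 composite clinical success with Simplify "is no more than 0.10 smaller than the probability of ACDF control patients achieving Month 60 CCS". The study then succeeds if the propensity-score-adjusted, imputation-based "1-sided p-value for rejecting this null hypothesis is less than or equal to 0.05".

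Other sections indicate what the test is meant to show:

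- Section 2.3.2 gives the research hypothesis that the Month 60 success "rate of the Simplify Disc will be no worse than conventional ACDF". Section 2.3.7.1 repeats it. Neither states a margin or a null.
- Section 2.3.7.4 works with a lower confidence bound: "The lower bound of the 90% 2-sided CI is equivalent to the lower bound of the 95% 1-sided non-inferiority CI".
- Section 2.3.7.5 reports that "the power to detect non-inferiority is 96% at a one-sided 0.05 significance level". It does not repeat the margin.
- Section 2.3.7.6 calls the Section 2.3.7.2 rule the non-inferiority criterion and allows superiority testing only once it is met.

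**The concern.** Write pS and pC for the Month 60 success probabilities with Simplify and ACDF, and d = pS − pC. The words "no more than 0.10 smaller" mean d ≥ −0.10. That is the region in which Simplify is non-inferior, which is what the study hopes to establish. In a non-inferiority test this region belongs in the alternative. Here it is the null, and success depends on rejecting it. The complement is d < −0.10, so the written rule asks for evidence that Simplify falls short of ACDF by more than the margin.

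Section 2.3.7.2 is the pre-specified success criterion of a post-approval study and the gate to the superiority claim. The tipping-point analyses in Section 2.3.7.7, which count scenarios where the conclusion changes, rely on the same rule. If the text stays, the analyst must depart from the written criterion to run the intended test, and must justify that departure after the Month 60 data are known.

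**Working it through.** **Inputs.** Margin 0.10 and one-sided alpha 0.05 (Section 2.3.7.2). Sample sizes 121 and 64, success rates 65% and 50% (Section 2.3.7.5). Month 24 adjusted difference 19.4 points with 90% lower bound 10.9 points (Section 2.3.7.4). The calculations use the normal approximation for two independent proportions and ignore propensity-score stratification and imputation.

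**Standard error at the planning values.**
SE = √(0.65×0.35/121 + 0.50×0.50/64) = √(0.001880 + 0.003906) = 0.0761.

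**Step 1: reproduce the plan's power with the conventional null (H0: d ≤ −0.10).**
Power = Φ((d + 0.10)/SE − 1.645) = Φ(0.25/0.0761 − 1.645) = Φ(1.64) = 0.950.
A pooled null variance also gives 95.0%, and the Farrington-Manning restricted variance gives 95.3%. The plan states 96% without naming its method, so the agreement is within about one point.

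**Step 2: apply the rule as written (H0: d ≥ −0.10, rejected for small d).**
P(success) = Φ(−(d + 0.10)/SE − 1.645) = Φ(−3.29 − 1.645) = Φ(−4.93) ≈ 4 × 10⁻⁷.
With this SE, success needs an observed difference below −0.10 − 1.645×0.0761 = −0.225, that is, Simplify more than about 22.5 points worse. The stated power cannot be obtained from this null.

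**Step 3: compare both rules across true differences** (ACDF at 50%, 121 and 64 subjects, SE recomputed each time).

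| True d | P(success), rule as written | P(success), conventional rule |
|---|---|---|
| +0.15 | 0.0000004 | 0.950 |
| 0 | 0.0016 | 0.363 |
| −0.10 | 0.05 | 0.05 |
| −0.20 | 0.377 | 0.0015 |
| −0.30 | 0.869 | 0.000005 |

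The result does not depend on the 50% control rate. With ACDF at 60% and Simplify at 30% (illustrative values, not from the plan), SE = √(0.30×0.70/121 + 0.60×0.40/64) = 0.0741, and the rule as written gives Φ(0.20/0.0741 − 1.645) ≈ 0.85.

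**Step 4: run the Month 24 result through both rules.**
Implied SE = (19.4 − 10.9)/1.645 = 5.17 points, and z = (19.4 + 10)/5.17 = 5.69. The one-sided p-value against the conventional null is about 6 × 10⁻⁹. The p-value for rejecting the null as written is 1 minus that, above 0.9999. A result that clearly favours Simplify would fail the written criterion.

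**The case against.** The strongest reply is that nobody would run the test as written. The research hypothesis is non-inferiority, a lower confidence bound is of no use in a test that looks for inferiority, the power statement names non-inferiority, and Section 2.3.7.6 gives the criterion its proper name. Requiring proof of inferiority before testing superiority would make no sense. On this view the sentence is a transposition of null and alternative, and the probabilities in Steps 2 and 3 describe a test that nobody planned.

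Most of this stands. The intent is clear, a competent analyst would probably run the intended test, and the figures for the written rule measure how far the text departs from that intent. They are not a forecast of what will happen. Section 2.3.2 also states only a research hypothesis and says nothing about rejecting a null, so its conflict with Section 2.3.7.2 is one of direction only.

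The reply does not rescue the sentence. No other section states the primary null or the 0.10 margin, so a reader looking for the formal rule finds only the reversed one. A pre-specified success criterion should not have to be corrected by inference from its neighbours.

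**Conclusion.** The decision rule in Section 2.3.7.2 is wrong as written and must be corrected. Null and alternative are exchanged, and the section conflicts with Sections 2.3.2, 2.3.7.1, 2.3.7.4, 2.3.7.5 and 2.3.7.6. Under the plan's own assumptions, the written rule reduces the chance of success from about 95% to about 4 × 10⁻⁷, and it rewards a device that is substantially worse than control. The direction of the error follows from the wording alone. Only the probabilities rest on the normal approximation and on leaving out stratification and imputation, and neither of those could reverse the direction.

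**What to change.** Restate Section 2.3.7.2 along these lines:

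- H0: pS − pC ≤ −0.10 (the Simplify Month 60 success probability is lower than that of ACDF by 0.10 or more).
- H1: pS − pC > −0.10.
- The study succeeds if H0 is rejected at one-sided 0.05 in the propensity-score-adjusted, multiply imputed analysis. Equivalently, the lower bound of the two-sided 90% confidence interval for pS − pC from that analysis lies above −0.10.

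The confidence-interval form agrees with the equivalence already given in Section 2.3.7.4. Repeating the 0.10 margin in Section 2.3.7.5 would let the power statement be checked on its own.

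The cost is a short wording change in one section. Margin, alpha, endpoint, adjustment, imputation, sample size and data collection stay the same. It should be made before the Month 60 comparison is run.

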#### 2.3.7.3 DESIGN OF THE OBSERVATIONAL STUDY

One hundred sixty-six (166) subjects were enrolled in the Simplify Disc IDE population. Of these, 16 Simplify Disc subjects were training subjects. The historical ACDF control population included 133 subjects. The 283 available subjects (150 Simplify Disc (excluding training subjects) and 133 historical ACDF control) were assessed via the Propensity Score (PS) sub-classification process. After applying an established heuristic for 3 iterations (6 models), a total of 150 Simplify Disc and 117 historical ACDF control subjects were retained in the final PS designed sample. Analysis of subject demographic and baseline data showed no meaningful differences between the treatment groups. The PS-selected population and PS sub classes defined in the IDE study will be utilized for the purposes of this study. Per the exclusion criteria, additional subjects are not enrolled into the PAS due to reasons that preclude long-term Simplify Disc data collection (e.g., SSI).

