### **2.3.7.6 SUPERIORITY TESTING**

If the non-inferiority study success criterion is met, superiority testing will be performed in the primary analysis set. It will be concluded that the Simplify Disc is superior to the ACDF control if the PS-quintile adjusted one-sided p-value determined from the multiple imputation is less than 0.05.

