#### 2.3.7.7 ADDRESSING MISSING PRIMARY OUTCOME DATA

Because of the availability of subject level data in controls that correspond to the subject level data to be collected in the prospective study, missing data will be addressed in the same fashion to how missing data would have been addressed in a randomized clinical trial. Multiple imputation will be used to impute missing final NDI in patients otherwise evaluable for primary CCS. For each of 20 imputed data sets, the primary PS stratified device group difference will be made resulting in a standard error for each. The final device group difference will be the average of the multiple imputed datasets and its standard error will account for both within (usual) and between imputation error.

In addition to multiple imputation, sensitivity analysis will be provided based on tipping point analyses. These are analyses in which all possible combinations of successes and failures are assumed for patients missing primary CCS and the fraction of scenarios in which the statistical conclusion changes is summarized. Best case and worst case, all missing success, and all missing failures scenarios will also be summarized.

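### The primary and superiority comparisons adjust only for PS subclasses fixed on the IDE sample, with no baseline NDI term and no balance recheck, although success is a change from baseline NDI

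*Combined protocol and SAP*

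**What the plan says.** - **Primary test (2.3.7.2).** The study is "a success if the PS-quintile adjusted, multiple imputation based, 1-sided p-value for rejecting this null hypothesis" "is less than or equal to 0.05". The margin is 0.10 on the difference in Month 60 success.
- **Superiority (2.3.7.6).** If non-inferiority is met, superiority is concluded when the "PS-quintile adjusted one-sided p-value determined from the multiple imputation is less than 0.05".
- **Estimator (2.3.7.7).** In each of 20 imputed data sets, "the primary PS stratified device group difference will be made resulting in a standard error for each". The results are then averaged, with within- and between-imputation error combined.
- **Subclasses (2.3.7.3).** "The PS-selected population and PS sub classes defined in the IDE study will be utilized for the purposes of this study". They were built on 150 Simplify and 117 control subjects. The section reports no meaningful baseline differences after that design step.
- **Endpoint (2.3.7.1).** One component of success is "Improvement on the NDI of at least 15 percentage points compared to baseline".
- **Who is expected at Month 60 (2.3.4, 2.3.7.5).** The study includes up to 142 Simplify and 106 control subjects. It expects 85% of the 142 (121), and for the other arm, "It is estimated that 60% of the estimated 106 (N=64) Control subjects".

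The readable text names no other covariate in the outcome comparison and does not list the PS covariates. It plans no balance table for the post-approval set.

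**The concern.** This is a non-randomised comparison with a historical control, so PS subclassification carries the whole burden of comparability. Five classes balance a covariate only coarsely, and differences within a class can remain. The one balance statement follows the 150/117 design sample. The set analysed five years on will be smaller, and unequally so, because of non-consent, exclusion for index-level surgery during the IDE, and dropout.

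Baseline NDI matters more than most covariates here. It enters the endpoint by subtraction and limits how far a subject can improve, so it very probably predicts success within PS classes. It must be on file for every subject scored on the NDI component.

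Two things are at stake. A residual baseline NDI difference would move the estimated success difference against a margin of only 10 points. Even with perfect balance, leaving out a predictor of the outcome costs precision, which matters more for superiority than for non-inferiority.

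**Working it through.** **Inputs from the documents.** Month 60 numbers 121 and 64, success 65% and 50%, and stated power 96% (2.3.7.5). Margin 0.10 and one-sided 0.05 (2.3.7.2). Design sample 150/117 (2.3.7.3).

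**1. The plan's own power.**
SE = √(0.65×0.35/121 + 0.50×0.50/64) = 0.0761.
Non-inferiority power = Φ((0.15 + 0.10)/0.0761 − 1.645) = 95.0%, which agrees with the stated 96% to within about a point.
Superiority power, by the same formula without the margin, = Φ(0.15/0.0761 − 1.645) = 62.8%.
Both ignore stratification and imputation variance.

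**2. Share of the balanced sample expected at Month 60.** Simplify 121/150 = 81%; control 64/117 = 55%.

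**3. How a residual shift acts on the error rate.** At the margin, take control 50% and Simplify 40%.
SE = √(0.40×0.60/121 + 0.50×0.50/64) = 0.0767.
Error = Φ(b/0.0767 − 1.645), where b is the bias in the risk difference. The values of b are assumed; none is in the documents.

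| b (positive favours Simplify) | One-sided error |
|---|---|
| −0.05 | 1.1% |
| −0.02 | 2.8% |
| 0 | 5.0% |
| +0.02 | 8.3% |
| +0.03 | 10.5% |

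The superiority test gives nearly the same figures.

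**4. What baseline imbalance could produce such a shift.** Assume a logit slope of success on baseline NDI of 0.4 to 0.85 per SD and a within-class imbalance of 0.2 SD. To first order the shift is slope × 0.2 × p(1−p). With p(1−p) = 0.24 this is 0.4×0.2×0.24 = 1.9 points up to 0.85×0.2×0.24 = 4.1 points.

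Simulation averages over the spread of NDI and so gives slightly less. The settings were 3,000 trials each, 121/64, a true difference of −10 points and complete data. Assumed class shares were 29/24/20/16/11% for control and 13/17/20/23/27% for Simplify.

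| Within-class imbalance favouring Simplify | Shift, points | Error, PS classes only |
|---|---|---|
| none | – | 6.2–6.5% |
| 0.1 SD | 1.0–1.7 | 7.1–9.6% |
| 0.2 SD | 1.8–3.5 | 8.9–12.3% |

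With baseline NDI in the model the error was about 4 to 6%. At 142/106 and 0.2 SD, 8.6–15.0% fell to 4.2–5.6%. Ranges cover the two slopes and repeated runs.

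**5. How much of that error belongs to NDI.** With no imbalance the error already exceeds 5%. It is still 6.2% with an NDI slope of zero and plug-in stratum variances, and 5.4% with n−1 variances. The smallest control class has about 0.11×64 = 7 subjects. So roughly 1 point of the error comes from sparse strata and the variance formula, which the plan does not specify.

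**6. Precision with perfect balance.** Multiply the SE from step 1 by √(1−R²), where R² is the share of outcome variance that baseline NDI explains within classes. Values of about 0.05 to 0.15 follow from assuming a baseline SD of 14, a Month 60 SD of 20 and a correlation of about 0.14 to 0.42.

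| R² | Non-inferiority power | Superiority power |
|---|---|---|
| 0 | 95.0% | 62.8% |
| 0.05 | 95.8% | 64.7% |
| 0.15 | 97.3% | 68.9% |

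In simulation the empirical SE fell from about 0.082–0.084 to 0.074–0.079. Part of that gain comes from modelling the strata rather than from NDI.

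**The case against.** PS subclassification is an accepted primary method that keeps design separate from outcome modelling. The PS was built over three iterations and six models, and section 2.3.3 says FDA reviewed it. Keeping it makes Month 60 comparable with Month 24. The simulated imbalance is placed on the very covariate that the proposed model then includes, so adjustment was bound to succeed. The assumed success rates are labelled conservative, and the Month 24 adjusted difference was +19.4 points. On this view an NDI-adjusted sensitivity analysis would be enough.

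Much of this stands, and it rules out two stronger readings. A reader might infer that the plan ignores baseline NDI altogether. The documents do not support that: the PS covariates are not listed, so NDI may be among them, and section 2.3.7.3 reports no meaningful baseline differences. A reader might also infer that the tests are biased towards Simplify. No passage shows a residual imbalance, and one in the other direction would make the tests conservative.

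The objection does not answer three things. Five classes can leave within-class differences even in a covariate that is in the PS. Balance at 150/117 does not guarantee balance in a set that keeps about 81% and 55%; those are planning estimates, but the plan's own. Finally, imputation covers only a missing final NDI in otherwise evaluable subjects, and the tipping-point analyses vary missing outcomes. Neither restores baseline balance.

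**Conclusion.** The concern holds as a gap in robustness and efficiency, not as a demonstrated bias or an arithmetic error. The documents establish four facts: adjustment is by PS subclass alone, the classes are fixed on the IDE sample, success is a change from baseline NDI, and the readable text plans no balance recheck.

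The size rests on assumptions. If baseline NDI has a logit slope of 0.4 to 0.85 per SD and differs by 0.2 SD within classes in Simplify's favour, the shift is about 2 to 3.5 points, a fifth to a third of the margin. One-sided error is then about 9 to 12%, including roughly 1 point from sparse strata. The sign and size of any real imbalance are unknown.

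The precision gain is modest: about 1 to 3 points of non-inferiority power and 2 to 6 of superiority power. The change is worth making because it is nearly free.

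**What to change.** Amend 2.3.7.2, 2.3.7.6 and 2.3.7.7, and fix the wording before Month 60 outcomes are compared:

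1. In each imputed data set, fit a logistic model of Month 60 success on device, PS subclass and continuous baseline NDI. Average the predicted risks over the analysis set under each device to obtain the marginal risk difference, with a robust SE.
2. Combine by Rubin's rules and test against −0.10 and then against 0, as now.
3. Keep the plain PS-stratified difference as a sensitivity analysis, for comparability with Month 24, and state its variance formula.
4. Tabulate baseline balance, including NDI, by PS subclass in the post-approval analysis set before outcomes are compared.
5. State whether baseline NDI is a PS covariate.

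The cost is SAP wording and a few lines of code, with no new data. The downsides are mild model dependence and a primary estimator that differs from the Month 24 one; item 3 lets a reader judge both.

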#### 2.3.7.3 DESIGN OF THE OBSERVATIONAL STUDY

One hundred sixty-six (166) subjects were enrolled in the Simplify Disc IDE population. Of these, 16 Simplify Disc subjects were training subjects. The historical ACDF control population included 133 subjects. The 283 available subjects (150 Simplify Disc (excluding training subjects) and 133 historical ACDF control) were assessed via the Propensity Score (PS) sub-classification process. After applying an established heuristic for 3 iterations (6 models), a total of 150 Simplify Disc and 117 historical ACDF control subjects were retained in the final PS designed sample. Analysis of subject demographic and baseline data showed no meaningful differences between the treatment groups. The PS-selected population and PS sub classes defined in the IDE study will be utilized for the purposes of this study. Per the exclusion criteria, additional subjects are not enrolled into the PAS due to reasons that preclude long-term Simplify Disc data collection (e.g., SSI).

